6.2.5. Cabozantinib Administration outside the Clinic

The subject should take cabozantinib outside the clinic at approximately the same time every day, preferentially before going to bed, and should adhere to the fasting requirements described in this section.

Subjects are to fast (with the exception of water) for at least 2 hours after eating the evening meal before taking their dose. After the 2-hour fast and before going to bed, subjects are to take cabozantinib with a full glass of water (minimum of 8 oz or 240 mL) with no food intake for one more hour post-dose. If the subject's schedule requires taking cabozantinib during the day, the subject is to be instructed to follow the same fasting recommendations.

Tablets should not be crushed or chewed. Grapefruit and Seville oranges (and products made from them) should be avoided while being treated with cabozantinib.

Subjects are to be instructed to not make up vomited doses and to maintain the planned dosing schedule. Subjects are not to make up for missed doses if more than 12 hours have elapsed after the time the subject would usually take cabozantinib. In the event of missed doses, subjects are not to take 2 doses to make up for the one the subject missed.

Any unused study treatment must be returned to the study site for drug accountability and disposal.

6.2.6. Sorafenib Administration outside the clinic

Sorafenib should be taken orally twice daily at the same time each day. Sorafenib should be taken either without food or with a low-fat or moderate fat meal. If a subject intends to have a high fat meal, sorafenib should be taken at least 1 hour before or 2 hours after the meal.

Sorafenib tablets should be swallowed whole with a glass of water. Subjects should be instructed that if a dose of sorafenib is missed, the next dose should be taken at the regularly scheduled time, and the subject should not double the dose. Refer to the current sorafenib label appropriate to the respective site location for additional details regarding dosage and administration.

6.3. Treatment after Study Completion

After study completion (see [Section 3.5.3](#)), subjects who continue to demonstrate clinical benefit may be eligible to receive Exelixis-supplied study treatment for the maximum treatment duration specified in [Section 6.2](#) during the Maintenance Phase. Alternatively, study treatment may be provided via a rollover study requiring approval by responsible health authority and ethics committee or through another mechanism at the discretion of Exelixis.

Exelixis reserves the right to terminate access to Exelixis-supplied study treatment if any of the following occur:

- a) The study is terminated due to safety concerns.
- b) The development of atezolizumab or cabozantinib is terminated for other reasons, including but not limited to lack of efficacy and/or not meeting the study objectives (eg, the null hypothesis is not rejected for the primary endpoint of OS).
- c) The participant can obtain medication from a government-sponsored or private health program.

In all cases Exelixis will follow local regulations. Exelixis will work with study investigators to act in the best interest of subjects.

6.4. Compliance

Subject compliance with outpatient study treatment will be assessed by the site using drug dispensing and return records, infusion logs, progress notes about dose reductions/interruptions, and subject interview. These data will not be directly recorded in the CRF; rather, the CRF will capture infusion details and, for oral study treatment, intervals of constant dose and reasons for changes in dose level (eg, a new record completed each time dose level changes, including periods where no dose was taken, and the reason for a dose level change).

6.5. Study Treatment Accountability

The Investigator or designee will maintain accurate records of receipt of all study treatment including dates of receipt. In addition, accurate records will be kept regarding when and how much study treatment is dispensed and used by each subject in the study. Reasons for deviation from the expected dispensing regimen must also be recorded. Drug accountability will be performed periodically by the Sponsor or designee at interim monitoring visits. To satisfy regulatory requirements, at the time of site closure all unused study treatment will undergo final reconciliation and be destroyed according to applicable state, federal, and local regulations.

6.6. Safety Considerations

6.6.1. Management of AEs with Dose Reductions and/or Dose Interruptions

Subjects will be monitored for SAEs from the time of signing informed consent and for nonserious AEs from first dose of study treatment. Monitoring continues through 30 days (100 days for AESIs [Table 31] regardless of seriousness and for unrelated SAEs) after the date of the decision to permanently discontinue all study treatment (defined as the later of the date of the decision to discontinue all study treatment or the date of the last dose of any study treatment). Longer monitoring periods are required for related SAEs and certain other events as described in Section 8.4. Further details for follow-up and data collection requirements for AEs, SAEs, and AESIs are summarized in Appendix K. Subjects will be instructed to notify their physician immediately for any occurring AE. Causality assessment of AEs should include at minimum confounding factors such as disease and concomitant medications. Adverse event severity will be graded by the Investigator according to CTCAE v5.

The following should be taken into consideration in decisions regarding management for treatment-related side effects:

- Cabozantinib and atezolizumab have class-specific safety profiles based on their mechanism of action but may also cause AEs that overlap. For management of AEs in the experimental arm which can be clearly attributed to either cabozantinib or atezolizumab, independent dose modification for either agent is allowed.
 - Examples of VEGFR-TKI associated AEs caused by cabozantinib are hypertension and hand-foot syndrome.
 - Examples of AESIs caused by atezolizumab are pneumonitis and endocrinopathies.

For AEs without clear attribution to either study treatment, management of toxicity should include dose modifications of both agents per the discretion of the Investigator. Examples of overlapping AEs are diarrhea and transaminase increases.

- As a general approach all AEs should be managed with supportive care including both pharmacological and non-pharmacological treatments according to consensus management guidelines at the earliest signs of toxicity considered related to study treatment.
- Study treatment may be continued for mild AEs if appropriate supportive care has been initiated to ameliorate symptoms. Should this be ineffective and toxicities become

unacceptable, dose modifications of study treatment should be considered to prevent worsening of toxicity. Moderate to severe AEs usually require dose modifications including dose reductions and/or interruptions.

- Dose interruptions of cabozantinib or atezolizumab for AEs may occur at any time and independently at the discretion of the Investigator. If both study treatments in the experimental arm or sorafenib in the comparator arm are interrupted for more than 12 weeks, treatment should be discontinued unless approved by the Sponsor. Dose interruptions of sorafenib for AEs may also occur at any time at the discretion of the Investigator.
- Subjects on the experimental arm (cabozantinib + atezolizumab) will be allowed to discontinue one component of the study treatment but continue to receive the other; the Investigator is encouraged to discuss such circumstances with the Sponsor.

Cabozantinib:

- The assigned dose for cabozantinib in the experimental combination arm is 40 mg qd. Escalation of cabozantinib from 40 mg qd to 60 mg qd is allowed after Sponsor approval for subjects who are tolerating the 40 mg cabozantinib dose level well and have been treated on this dose level for at least 4 weeks. In general, subjects who develop clinically relevant adverse events (eg, Grade 3 or 4 AEs) are not allowed to dose escalate cabozantinib from 40 mg qd to 60 mg qd. The assigned dose for cabozantinib in the single-agent cabozantinib arm is 60 mg qd.
- Two dose reduction levels of cabozantinib (20 mg daily, and 20 mg every other day [qod]) are permitted on the experimental combination arm (see [Table 7](#)).
Note: Subjects who have their dose escalated to 60 mg on the experimental arm would be permitted to reduce dose back to 40 mg before further reduction to lower dose levels.
- Two dose reduction levels of cabozantinib (40 mg daily, 20 mg daily) are permitted on the single-agent cabozantinib arm (see [Table 7](#)).
- Dose modification criteria for treatment-related AEs of cabozantinib are shown in [Table 8](#).
- Dose reinstitution and reescalation after dose interruptions and/or reductions:
 - If the subject recovers from his or her toxicities to \leq Grade 1 per CTCAE v5 or to the baseline value (or lower) and the AE was unrelated to cabozantinib, then cabozantinib may be restarted with no change in dose.

- If the subject recovers from his or her toxicities to \leq Grade 1 or to the baseline value (or lower) and the AE was deemed possibly related to cabozantinib, then cabozantinib may be restarted at a reduced dose (see [Table 8](#)). Subjects who initiated treatment with cabozantinib at 40 mg and experience a possibly related AE of Grade 1 or 2 severity may be restarted with no dose change after recovery of the toxicities to \leq Grade 1 or to the baseline value (or lower) if appropriate supportive care can prevent or minimize the risk of the AE.
- Subjects receiving a dose of 20 mg qod on the experimental combination arm (20 mg qd on the single-agent cabozantinib arm) who have cabozantinib interrupted may be restarted at the same dose if deemed safe at the discretion of the Investigator. Subjects unable to tolerate a dose of 20 mg qod (20 mg qd on the single-agent cabozantinib arm) must discontinue cabozantinib.
- Reescalation to the previous dose may be allowed at the discretion of the Investigator for AEs which have resolved or recovered to Grade 1 (or baseline value) and deemed tolerable and easily managed by optimized supportive treatment. Dose reescalation is not allowed following a cabozantinib-related dose reduction for Grade 4 AEs affecting major organs (eg, CNS, cardiac, hepatic, renal, pulmonary, GI).
- Guidelines for the management of specific AEs of cabozantinib such as GI disorders, non-GI fistula formation, hemorrhage, thromboembolic events, hypertension, stomatitis and mucositis, skin disorders, osteonecrosis, proteinuria, nervous system disorders, hepatocellular toxicity, infections and infestations, blood system disorders, fatigue, weight loss, QTc prolongation, electrolyte disorders, endocrine disorders, and respiratory disorders are provided in [Section 6.6.2.1](#).

Table 7: Dose Levels of Cabozantinib (Oral Dosing)

Assigned Starting Dose	First Dose Level Reduction	Second Dose Level Reduction	Third Dose Level Reduction
40 mg daily (qd) ^a (Experimental arm)	20 mg daily (qd)	20 mg every other day (qod) ^b	No dose reduction permitted
60 mg daily (qd) (Single-agent cabozantinib arm)	40 mg daily (qd)	20 mg daily (qd) ^c	No dose reduction permitted

^a Subjects who have their dose escalated to 60 mg on the experimental arm would be permitted to reduce dose back to 40 mg before further reduction to lower dose levels.

^b Cabozantinib will be discontinued on the experimental if a dose of 20-mg cabozantinib every other day is not tolerated.

^c Cabozantinib will be discontinued on the single-agent cabozantinib arm if a qd dose of 20 mg cabozantinib is not tolerated

Table 8: Dose Modifications for Cabozantinib-Related AEs

CTCAE v5 Grade	Recommended Guidelines for Management ^a
Grade 1 AEs	Add supportive care as indicated. Continue cabozantinib at the current dose level if AE is manageable and tolerable.
Grade 2 AEs which are tolerable and are easily managed	Continue cabozantinib at the current dose level with supportive care.
Grade 2 AEs which are intolerable and cannot be adequately managed	Cabozantinib should be dose reduced or interrupted. Note: It is recommended that dose interruptions be as brief as possible.
Grade 3 AEs (except clinically non-relevant laboratory abnormalities)	Cabozantinib should be interrupted unless the toxicity can be easily managed with a dose reduction of cabozantinib and optimal medical care. Note: It is recommended that dose interruptions be as brief as possible.
Grade 4 AEs (except clinically non-relevant laboratory abnormalities)	Cabozantinib must be interrupted immediately. In general, cabozantinib should be discontinued unless the following criteria are met: 
• Subject is deriving clear clinical benefit as determined by the investigator and agreed by the Sponsor• Toxicity can be managed with a dose reduction of cabozantinib following recovery to Grade 1 (or baseline) and optimal medical care Sponsor must be contacted to discuss treatment continuation upon resolution of AEs.

AE, adverse event.

Note: Cabozantinib dose modification criteria for specific medical conditions are provided in [Section 6.6.2.1](#).

Atezolizumab:

- The assigned dose for atezolizumab is 1200 mg IV every 3 weeks. Infusion will occur every three weeks (\pm 2 days).
- Dose delays are allowed for atezolizumab (see [Table 9](#)), but dose reductions are not allowed.
- Dose modification criteria for irAEs and other AESIs and for guidance on reinstating atezolizumab are shown in [Table 10](#).
- If corticosteroids are initiated for treatment of irAEs, they must be tapered over \geq 1 month to \leq 10 mg/day oral prednisone or equivalent before atezolizumab can be resumed.
- Guidelines for the management of IRRs and CRS, irAEs for atezolizumab (ie, pneumonitis, hepatitis, diarrhea/colitis, myocarditis, endocrinopathies including hypophysitis, and infection) and other AESIs are provided in [Section 6.6.2.2](#).

Table 9: Dose Interruptions of Atezolizumab

Assigned dose	Dose Interruptions
1200-mg atezolizumab IV q3w	At any time to manage unacceptable AESIs

AESI, adverse events of special interest; q3w, once every 3 weeks;

Table 10: Dose Modifications for Atezolizumab-Associated Adverse Events

CTCAE v5 Grade	Recommended Management
Grade 1 immune-mediated myelitis*	Delay treatment with atezolizumab
Grade 1 pericarditis**	Treatment may be resumed in subjects following recovery to Grade 0-1
Grade 2 myocarditis	
Grade 1 ^a - 2 pneumonitis	* Continue atezolizumab unless symptoms worsen or do not improve.
Grade 2 nephritis	
Transaminases (ALT or AST):	** Withhold treatment with atezolizumab and conduct a detailed cardiac evaluation to determine the etiology and manage accordingly.
• Increases to between $> 3 \times$ ULN and $\leq 10 \times$ ULN (from baseline values \leq ULN), or	
• Increases to between $> 5 \times$ ULN and $\leq 10 \times$ ULN (from baseline values between $>$ ULN and $\leq 3 \times$ ULN), or	
• Increases to between $> 8 \times$ ULN and $\leq 10 \times$ ULN (from baseline values between $> 3 \times$ ULN and $\leq 5 \times$ ULN)	

CTCAE v5 Grade	Recommended Management
Grade 2 immune-mediated neuropathy (any cranial nerve disorder, including facial paresis, should be managed as per Grade 2 guidelines)***	Delay treatment with atezolizumab Treatment may be resumed in subjects following recovery to Grade 0-1.
Grade 2 or 3 diarrhea or colitis	
Grade 2 or 3 myositis	
Symptomatic adrenal insufficiency, hypothyroidism, or hyperthyroidism; Grade 2 or 3 hypophysitis; or Grade 3 or 4 hyperglycemia	*** For general immune-related neuropathy, if the event resolves to Grade 1 or better, resume atezolizumab. For facial paresis, if event resolves fully, resume atezolizumab; if event does not resolve fully while withholding atezolizumab, permanently discontinue atezolizumab.
Grade 2 ocular inflammatory toxicity	
Grade 2 or 3 pancreatitis or Grade 3 or 4 increases in amylase or lipase levels	
Grade 3 or 4 infection	
Grade 2 infusion-related reactions or cytokine release syndrome	
Grade 3 rash	
Suspected Stevens-Johnson syndrome or toxic epidermal necrolysis (any grade)	
Other Grade 2 or 3 atezolizumab-associated AEs	
Grade 2 - 4 immune-mediated myelitis	Permanently discontinue atezolizumab
Grade 3 or 4 immune-mediated neuropathy, including facial paresis	
Grade 2 - 4 myocarditis	
Grade 4 myositis and/or recurrent Grade 3 myositis	
Grade 3 or 4 pneumonitis	
Grade 3 or 4 nephritis	
AST or ALT $> 10 \times$ ULN or total bilirubin $> 3 \times$ ULN	
Grade 4 diarrhea or colitis	
Grade 4 hypophysitis and/or recurrent hypophysitis	
Myasthenic syndrome/myasthenia gravis, Guillain-Barré or meningoencephalitis (all grades)	
Grade 3 or 4 ocular inflammatory toxicity	
Grade 4, or recurrent Grade 2 or 3, immune-mediated pancreatitis	

CTCAE v5 Grade	Recommended Management
Grade 3 or 4 infusion-related reactions or cytokine release syndrome	
Grade 4 rash	
Confirmed Stevens-Johnson syndrome or toxic epidermal necrolysis (any grade)	
Other Grade 4 or recurrent Grade 3 atezolizumab-associated AEs	Permanently discontinue atezolizumab

AE, adverse event; AESI, adverse events of special interest; ALT, alanine aminotransferase; AST, aspartate aminotransferase; irAE, immune-related adverse event; ULN, upper limit of normal.

Note: Additional information for atezolizumab dose modification criteria and treatment recommendations for irAEs, infusion reactions, and other AESIs are provided in [Section 6.6.2.2](#).

^a Consider interrupting atezolizumab for Grade 1 pneumonitis.

^b Resumption of atezolizumab may be considered in patients who are deriving benefit and have fully recovered from the immune-mediated event. The decision to re-challenge patients with atezolizumab should be based on investigator's assessment of benefit–risk and documented by the investigator. The Medical Monitor is available to advise as needed.

Sorafenib:

- The assigned dose for sorafenib is 400 mg twice daily.
- When dose reduction is necessary, the sorafenib dose may be reduced to 400 mg once daily (qd). If additional dose reduction is required, sorafenib may be reduced to a single 400 mg dose every other day (qod).

For additional details on management guidance of AEs refer to the most current sorafenib prescribing information appropriate to the respective site location.

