6.6.2.2.11. Immune-Related Cardiac Events

Immune-Related Myocarditis

Immune-related myocarditis has been associated with the administration of atezolizumab. Immune-related myocarditis should be suspected in any subject presenting with signs or symptoms suggestive of myocarditis, including, but not limited to, laboratory (eg, B-type natriuretic peptide) or cardiac imaging abnormalities, dyspnea, chest pain, palpitations, fatigue, decreased exercise tolerance, or syncope. Myocarditis may also be a clinical manifestation of myositis and should be managed accordingly. Immune-related myocarditis needs to be distinguished from myocarditis resulting from infection (commonly viral, eg, in a subject who reports a recent history of gastrointestinal illness), ischemic events, underlying arrhythmias, exacerbation of preexisting cardiac conditions, or progression of malignancy.

All patients with possible myocarditis should be urgently evaluated by performing cardiac enzyme assessment, an ECG, a chest X-ray, an echocardiogram, and a cardiac MRI as appropriate per institutional guidelines. A cardiologist should be consulted. An endomyocardial biopsy may be considered to enable a definitive diagnosis and appropriate treatment, if clinically indicated.

Patients with signs and symptoms of myocarditis, in the absence of an identified alternate etiology, should be treated according to the guidelines in [Table 25](#).

Immune-Mediated Pericardial Disorders

Immune-mediated pericarditis should be suspected in any patient presenting with chest pain and may be associated with immune-mediated myocarditis (see section on myocarditis above).

Immune-mediated pericardial effusion and cardiac tamponade should be suspected in any patient presenting with chest pain associated with dyspnea or hemodynamic instability.

Patients should be evaluated for other causes of pericardial disorders such as infection (commonly viral), cancer related (metastatic disease or chest radiotherapy), cardiac injury related (post myocardial infarction or iatrogenic), and autoimmune disorders, and should be managed accordingly.

All patients with suspected pericardial disorders should be urgently evaluated by performing an ECG, chest X-ray, transthoracic echocardiogram, and cardiac MRI as appropriate per institutional guidelines. A cardiologist should be consulted. Pericardiocentesis should be considered for diagnostic or therapeutic purposes, if clinically indicated.

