Patients with signs and symptoms of pericarditis, pericardial effusion, or cardiac tamponade, in the absence of an identified alternate etiology, should be treated according to the guidelines in [Table 25](#). Withhold treatment with atezolizumab for Grade 1 pericarditis and conduct a detailed cardiac evaluation to determine the etiology and manage accordingly.

Table 25: Management Guidelines for Immune-Related Cardiac Events

Event	Management
Immune-related myocarditis, Grades 2-4	
• Permanently discontinue atezolizumab and contact the Sponsor.^a• Refer subject to cardiologist• Initiate treatment as per institutional guidelines and consider antiarrhythmic drugs, temporary pacemaker, ECMO, or VAD as appropriate.
Immune-related pericardial disorders, Grades 2-4	
• Initiate treatment with 1-2 mg/kg/day IV methylprednisolone or equivalent and convert to 1-2 mg/kg/day oral prednisone or equivalent upon improvement.• If event does not improve within 48 hours after initiating corticosteroids, consider adding an immunosuppressive agent.• If event resolves to Grade 1 or better, taper corticosteroids over \geq 1 month.

^a ECMO, extracorporeal membrane oxygenation; IV, intravenous; VAD, ventricular assist device.

Resumption of atezolizumab may be considered in subjects who are deriving benefit and have fully recovered from the immune-related event. The decision to rechallenge with atezolizumab should be based on investigator's assessment of benefit-risk, and documented by the investigator. The Medical Monitor is available to advise as needed.

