8.3. Adverse Events of Special Interest

Adverse events of special interest (AESIs) consist of immune-mediated AEs associated with ICIs, cases of potential DILI, and suspected transmission of an infectious agent by the study treatment ([Table 31](#)).

AESIs will be reported to the Sponsor or designee using the SAE reporting form irrespective of whether the event is serious or nonserious; all AESIs must be reported within 24 hours using the SAE process as described in [Section 8.2](#).

Guidance for management of immune-mediated AEs associated is provided in [Section 6.6.2.2](#) and can also be found in the local prescribing information and Investigator's Brochure for atezolizumab.

Table 31: Adverse Events of Special Interest

Category	Event
DILI	
Cases of potential DILI that include an elevated ALT or AST in combination with either an elevated bilirubin or clinical jaundice, as defined by Hy's Law and based on the following observations:
Treatment-emergent ALT or AST $> 3 \times$ baseline value in combination with total bilirubin $> 2 \times$ ULN (of which $\geq 35\%$ is direct bilirubin)Treatment-emergent ALT or AST $> 3 \times$ baseline value in combination with clinical jaundice
Other	
Suspected transmission of an infectious agent by the study treatment, as defined below
Any organism, virus, or infectious particle (eg, prion protein transmitting transmissible spongiform encephalopathy), pathogenic or non-pathogenic, is considered an infectious agent. A transmission of an infectious agent may be suspected from clinical symptoms or laboratory findings that indicate an infection in a patient exposed to a medicinal product. This term applies only when a contamination of study treatment is suspected.
irAE	
Pneumonitis
irAE	
Colitis
irAE	
Endocrinopathies: diabetes mellitus, pancreatitis, adrenal insufficiency, hyperthyroidism, and hypophysitis
irAE	
Hepatitis, including AST or ALT $> 10 \times$ ULN
irAE	
Systemic lupus erythematosus
irAE	
Neurological disorders: Guillain-Barré syndrome, myasthenic syndrome or myasthenia gravis, meningoencephalitis, myelitis, and facial paresis

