irAE	
Events suggestive of hypersensitivity, infusion-related reactions, cytokine release syndrome, influenza-like illness, hemophagocytic lymphohistiocytosis, and macrophage activation syndrome
irAE	
Nephritis
irAE	
Ocular toxicities (eg, uveitis, retinitis)
irAE	
Myositis
irAE	
Myopathies, including rhabdomyolysis
irAE	
\geq Grade 2 cardiac disorders
irAE	
Vasculitis
irAE	
Severe cutaneous reactions (eg, Stevens-Johnson syndrome, bullous dermatitis, toxic epidermal necrolysis)

ALT, alanine aminotransferase; AST, aspartate aminotransferase; DILI, drug-induced liver injury; irAE, immune-related adverse event; ULN, upper limit of normal.

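### Table 10 of the protocol both delays and permanently discontinues atezolizumab for Grade 2 myocarditis; the delay entry conflicts with Table 25 and should be deleted

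*Protocol*

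**What the plan says.** The atezolizumab bullets in Protocol Section 6.6.1 make Table 10 the reference for restarting the drug: "Dose modification criteria for irAEs and other AESIs and for guidance on reinstating atezolizumab are shown in" Table 10. The same bullets also refer sites to Section 6.6.2.2 for managing specific immune-related events, myocarditis among them.

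Table 10 has two blocks that matter here:

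- **Delay block.** It lists "Grade 2 myocarditis". The action is to delay atezolizumab, and dosing may restart after recovery to Grade 0-1.
- **Permanent-discontinuation block.** It lists "Grade 2 - 4 myocarditis".

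Section 6.6.2.2.11 states: "Patients with signs and symptoms of myocarditis, in the absence of an identified alternate etiology, should be treated according to the guidelines in" Table 25. The Table 25 row is "Immune-related myocarditis, Grades 2-4", and its only instruction for atezolizumab is permanent discontinuation with contact to the Sponsor. Footnote a to that table allows an exception: "Resumption of atezolizumab may be considered in subjects who are deriving benefit and have fully recovered from the immune-related event". The investigator must base that decision on a benefit-risk assessment and document it.

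**The concern.** A dose-modification table should give one default action for a given event and grade. For Grade 2 myocarditis, Table 10 gives two. A site that reads the delay block may restart atezolizumab when the event reaches Grade 0-1. A site that reads the later block, or Table 25, stops for good unless the subject has fully recovered and the investigator documents a benefit-risk decision. Both sites would be following the protocol as written.

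What is at stake is subject safety and uniform conduct in the experimental arm. Under the delay entry a subject could be re-dosed with Grade 1 myocarditis still present and without the documented decision that rechallenge requires.

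**Working it through.** No arithmetic applies. The check sets the listings side by side and asks whether any other text reconciles them.

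**1. The three listings that state an action for Grade 2 myocarditis**

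| Place | Entry | Default action | Condition for restart |
|---|---|---|---|
| Table 10, delay block | Grade 2 | Delay | Recovery to Grade 0-1 |
| Table 10, discontinuation block | Grades 2-4 | Permanently discontinue | Exception only: full recovery, deriving benefit, documented benefit-risk decision (Table 10 footnote b) |
| Table 25 | Grades 2-4 | Permanently discontinue, contact Sponsor | Exception only: same conditions (Table 25 footnote a) |

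Two of the three agree. The delay entry is the outlier. Footnote b has no visible marker in the body of Table 10 as we have it, so its link to the discontinuation block is inferred. Footnote a to Table 25 supports the rechallenge conditions without it.

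**2. Is the overlap deliberate?** Other events named in both blocks of Table 10 are kept apart in one of three ways:

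- By grade or threshold: myelitis 1 against 2-4; pneumonitis 1-2 against 3-4; nephritis, neuropathy, ocular toxicity and infusion reactions or cytokine release syndrome 2 against 3-4; diarrhea or colitis 2-3 against 4; rash 3 against 4; transaminases up to 10 × ULN against above 10 × ULN.
- By recurrence as well as grade: myositis, hypophysitis, pancreatitis.
- By certainty of diagnosis: suspected against confirmed Stevens-Johnson syndrome or toxic epidermal necrolysis.

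Myocarditis alone overlaps with no qualifier. The asterisked notes belong to myelitis, pericarditis and neuropathy. The two myocarditis entries are separate lines with different grade wording, so a broken table does not explain them.

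**3. Does other text reconcile the two entries?**

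- *The rechallenge footnotes* do not. They describe an exception after permanent discontinuation and ask for more than the delay block does.
- *The general advice in Section 6.6.2.2* to consider holding for most Grade 2 toxicities does not. It is limited to events that the later subsections do not cover, and myocarditis has its own subsection, 6.6.2.2.11.
- *A hold during diagnostic work-up* is not what the entry says. Where Table 10 means evaluation first, it says so, as for pericarditis. The myocarditis entry carries a restart rule instead.

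**4. Is the Grade 0-1 threshold a real difference?** Table 25 itself speaks of the event resolving to Grade 1 or better when it sets the steroid taper. The protocol therefore contemplates a residual Grade 1 state, which is not the same as full recovery.

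**5. Result of deleting the delay entry.** Grades 2-4 then have one action in Table 10, and it matches Table 25.

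**The case against.** The strongest case on the other side concedes that the two rows conflict and argues that little follows from it:

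- **The specific section is clear.** Table 10 is headed as recommended management, and its note refers readers to Section 6.6.2.2. The subsection there on myocarditis gives one answer and calls for a cardiologist. This stands, but it does not settle the matter, because Section 6.6.1 names Table 10 as the place for guidance on restarting, which is the decision in dispute.
- **Safeguards exist on either path.** Section 8.3 says that "all AESIs must be reported within 24 hours using the SAE process", and Table 31 includes "Grade 2 cardiac disorders" and above, so the Sponsor learns of each case quickly. Under Section 6.6.1, corticosteroids given for an immune-related event must be tapered over at least 1 month to 10 mg/day of prednisone or less before atezolizumab restarts. Both points stand and reduce the risk. Neither tells a site which restart rule applies.
- **The harm may be nominal.** The protocol does not reproduce the CTCAE grades for myocarditis, so the clinical distance between Grade 0-1 and full recovery cannot be measured from the documents. That is fair. The difference in wording remains, and so does the absence of a documented benefit-risk decision in the delay entry.
- **The event is uncommon and statistically inert.** This is agreed. It limits the weight of the point, not its correctness.

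**Conclusion.** The concern holds. Table 10 contradicts itself on Grade 2 myocarditis, and its delay entry contradicts Table 25. The protocol also shows which entry is wrong: two of the three listings, including the one in the dedicated section, call for permanent discontinuation.

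The scope is narrow. Both actions stop atezolizumab at onset, so the conflict concerns only the conditions for restarting. Before any Crossover Phase, only the experimental arm (at least 370 subjects) receives the drug. Section 8.3.1 places myocarditis among the less frequent immune-related events and no rate is given, so no case count is estimated. There is no effect on endpoints, alpha or power, and any effect on the SAP's safety tabulations is negligible. The correction should be made because it removes an avoidable safety risk at almost no cost.

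This rests on reading the two Table 10 entries as they appear in the current text, and on Table 25 as the intended rule because Section 6.6.2.2.11 directs myocarditis there.

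**What to change.** Delete the Grade 2 myocarditis entry from the delay block of Table 10 and leave every other row in that block as it is. Table 10 then agrees with its own Grade 2-4 row, Section 6.6.2.2.11 and Table 25. Any restart after Grade 2 myocarditis follows only the existing rechallenge provision: full recovery, continuing benefit and a documented benefit-risk decision. No new medical rule is introduced.

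Tell sites by clarification letter or in the next amendment. The cost is one deleted table entry and the notice; there is no statistical cost.
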